7.2. Contraindications to Subsequent Study Intervention(s) Administration

The eligibility for subsequent study intervention administration must be confirmed before administering any additional dose.

All exclusion criteria have to be re-checked to ensure that the participant is still eligible. In addition, participants who meet any of the criteria listed below should not receive additional dose of study intervention.

- Study participants who experience any SAE judged to be possibly or probably related to study intervention or non-study concomitant vaccine/product, including hypersensitivity reactions.
- Study participants who develop any new condition which, in the opinion of the investigator, may pose additional risk to the participant if she continues to participate in the study.
- Anaphylaxis following the administration of study intervention.
- Any condition that in the judgment of the investigator would make intramuscular injection unsafe.
- Occurrence of a new pIMD (see Table 21 for the list of pIMDs) or the exacerbation of an existing pIMD that, in the opinion of the investigator, expose the participant to unacceptable risk from subsequent vaccination. In such cases, the investigator should use his/her clinical judgment prior to administering the next dose of study intervention.

The participants who have become ineligible for subsequent study intervention administration should be encouraged to continue other study procedures, at the investigators' discretion. All

relevant criteria for discontinuation of study intervention administration must be recorded in the eCRF.

7.3. Participant Discontinuation/Withdrawal From the Study

A participant is considered to have withdrawn from the study if no new study procedure has been performed or no new information has been collected for her since the date of withdrawal/last contact.

From an analysis perspective, a study "withdrawal" refers to any participant who did not return for the concluding visit.

Investigators will attempt to contact participants who do not return for scheduled visits or follow-up.

All data and samples collected up to and including the date of withdrawal of/last contact with the participant will be included in the study analyses.

The primary reason for study withdrawal will be documented in the eCRF based on the list below:

- AEs requiring expedited reporting to IQVIA
- Unsolicited non-serious AEs
- Solicited AE
- Withdrawal by participant, not due to an AE*
- Migrated/moved from the study area
- Lost to follow-up
- Sponsor study termination
- Other (specify)

*If a participant is withdrawn from the study because she withdrew consent and the reason for withdrawal was provided, the investigator must document this reason in the eCRF.

Participants who are withdrawn from the study because of AEs/SAEs must be clearly distinguished from participants who are withdrawn for other reasons. Investigator will follow participants who are withdrawn from the study due to an AE/SAE until the event is resolved.

7.4. Lost to Follow-up

A participant will be considered "lost to follow-up" if she fails to return for scheduled visits and is unable to be contacted by the study center. Refer to the SRM for a description of the actions to be taken before considering the participant as lost to follow-up.

8. STUDY ASSESSMENTS AND PROCEDURES

Protocol waivers or exemptions are only permitted when necessary for the management of immediate safety concerns for the participant.

Immediate safety concerns should be discussed with IQVIA as soon as they occur or when the study team becomes aware of them. The purpose of this communication is to determine if the participant(s) should discontinue the study intervention.

Study procedures and their timing are summarized in the schedule of activities (SoA) (Section 1.3).

All eligibility evaluations must be completed, and the results reviewed before confirming that potential participants meet all eligibility criteria.

The SRM provides the investigator and study center personnel with detailed administrative and technical information that does not impact the participant safety.

8.1. Immunogenicity Assessments

8.1.1. Biological Samples

Collected biological samples will be used for protocol-mandated research and purposes related to the improvement, development and quality assurance of the laboratory tests described in this protocol.

Additional serological assays may be performed in the future to further characterize the disease and/or the immunological response elicited by study intervention. These assays may not be represented in the objectives/endpoints of the study protocol.

Findings in this or future studies may make it desirable to use samples acquired in this study for research not planned in this protocol. In this case, all participants in countries where this is allowed will be asked to give consent to allow GSK or a contracted partner, to use the samples for further research. The further research will be subject to prior IEC/IRB approval, if required by local legislation.

Information on further investigations and their rationale can be obtained from GSK.

Sample testing will be done in accordance with the recorded consent of the individual participant/participant's parent(s)/LAR(s).

Collected samples will be stored for a maximum of 20 years. This storage period begins when the last participant performed the last study visit, unless local rules, regulations or guidelines require different timeframes or procedures, which would then be in line with participant consent. These extra requirements need to be communicated formally to and discussed and agreed with GSK.

Blood samples will be collected from participants as described in Table 7.

Table 7Biological Samples

Sample Type	Quantity	Time point	-	_	Time Point	Time Point	Time Point	_	Subset Name
Blood sampling for antibody determination	Approximately 50 mL	Visit 1 Day 1			Visit 4 Month 3			Visit 7 Month 12	All participant s
Blood sampling for any hematological/biochemical laboratory abnormality	Approximately 5 mL	Visit 1 Day 1	Visit 2* Day 7						Step 1 participant s

^{*}Visit 2 is for Step 1 participants only.

8.1.2. Laboratory Assays for Immunogenicity

The laboratory tests for immunogenicity are listed in Table 8 and Table 9. All laboratory testing will be performed at GSK laboratory or in a laboratory designated by GSK. Refer to Appendix 3 for a brief description of the assays.

Table 8 Humoral Immune Response

Assay type	System	Component	Method
Humoral Immunity	Serum	Anti-HPV-6 L1 VLP Ab IgG	ECL
(Antibody	Serum	Anti-HPV-11 L1 VLP Ab IgG	ECL
determination)	Serum	Anti-HPV-16 L1 VLP Ab IgG	ECL
	Serum	Anti-HPV-18 L1 VLP Ab IgG	ECL
	Serum	Anti-HPV-31 L1 VLP Ab IgG	ECL
	Serum	Anti-HPV-33 L1 VLP Ab IgG	ECL
	Serum	Anti-HPV-45 L1 VLP Ab IgG	ECL
	Serum	Anti-HPV-52 L1 VLP Ab IgG	ECL
	Serum	Anti-HPV-58 L1 VLP Ab IgG	ECL
	Serum	Anti-HPV-6 PSV L1/L2 neutralizing Ab	PBNA
	Serum	Anti-HPV-11 PSV L1/L2 neutralizing Ab	PBNA
	Serum	Anti-HPV-16 PSV L1/L2 neutralizing Ab	PBNA
	Serum	Anti-HPV-18 PSV L1/L2 neutralizing Ab	PBNA
	Serum	Anti-HPV-31 PSV L1/L2 neutralizing Ab	PBNA
	Serum	Anti-HPV-33 PSV L1/L2 neutralizing Ab	PBNA
	Serum	Anti-HPV-45 PSV L1/L2 neutralizing Ab	PBNA
	Serum	Anti-HPV-52 PSV L1/L2 neutralizing Ab	PBNA
	Serum	Anti-HPV-58 PSV L1/L2 neutralizing Ab	PBNA

Ab = antibody; ECL= electrochemiluminescence assay; HPV = human papilloma virus; IgG = immunoglobulin G; PBNA = pseudovirion-based neutralization assay; PSV = pseudovirion; VLP = virus-like particle

Further laboratory testing related to the investigational adjuvanted vaccine formulations and/or HPV disease may be performed if deemed necessary or if assay(s) become available.

The addresses of clinical laboratories used for sample analysis will be provided in a separate document accompanying this study protocol.

GSK clinical laboratories have established a Quality System supported by procedures. The activities of GSK clinical laboratories are audited regularly for quality assessment by an internal (GSK-dependent) but laboratory-independent Quality Department.

8.1.3. Immunological Correlates of Protection

There is no established correlate of protection with the assay(s) to be used in this study for any of the vaccines administered in the frame of this study.

8.2. Safety Assessments

The investigator and his/her designees are responsible for detecting, documenting, and reporting events that meet the definition of an AE or SAE. The investigator and designees are responsible

for following up AEs that are serious, considered related to the study intervention or the study, or that caused the participant's withdrawal from the study intervention or study.

8.2.1. Pre-Intervention Administration Procedures

8.2.1.1. Collection of Demographic Data

Demographic data such as age in years, race, and ethnicity (with attention to local ethical considerations) will be collected from each participant and recorded in the eCRF.

8.2.1.2. Collection of Medical/Vaccination History

The medical and vaccination history should be checked by interviewing the participant/participant's parent(s)/LAR(s) and/or review of the participant's medical records. It should be verified that none of the exclusion criteria related to medical and vaccination history (Section 5.2) are met. Any pre-existing conditions or signs and/or symptoms present in a patient prior to the first study vaccination will be recorded in the eCRF.

8.2.1.3. Physical Examination/Vital Signs

On Day 1, a history directed physical examination (including the injection site examination) will be performed for each participant as per the standard of care. Physical examination at each study visit after the first study intervention administration will be performed only if the participant's parent(s)/LAR(s) indicates during questioning that there might be some underlying pathology(ies) or if deemed necessary by the investigator or delegate. Collected information needs to be recorded in the eCRF.

On Day 1 and at each vaccination, vital signs (including temperature, systolic/diastolic blood pressure, heart rate, and respiratory rate after at least 10 minutes of rest) will be collected. Vital signs are to be taken before blood collection for laboratory tests. Collected information needs to be recorded in the eCRF

Treatment of any abnormality observed during this examination has to be performed according to local medical practice outside this study or by referral to an appropriate healthcare provider.

If the investigator determines that the participant's health on the day of study intervention administration (Visit 1 [Day 1], Visit 3 [Month 2] and Visit 5 [Month 6]) temporarily precludes dosing, the visit will be rescheduled. Refer to Section 5.4 for the list of criteria for the temporary delay of study intervention administration.

8.2.1.4. Pregnancy Test

All study participants must perform a high sensitivity urine pregnancy test prior to each study vaccine administration. Pregnancy testing must be performed even if the participant is denying

any sexual activity, menstruating at the time of visit, or is considered infertile. The study vaccine may only be administered after the pregnancy test is negative.

Refer to Appendix 5 for the contraceptive guidance and information on study continuation for a participant who becomes pregnant during the study.

8.2.1.5. Checking Contraindications, Warnings, and Precautions to Intervention Administration

Warnings and precautions to administration of study intervention must be checked at each visit with planned administration of study intervention. Refer to Section 7.2 for contraindications to subsequent study intervention administration and to Section 5.4 for criteria for temporary delay for enrollment and/or intervention administration.

8.2.2. Clinical Safety Laboratory Tests

Blood sampling for any hematological/biochemical laboratory abnormality for Step 1 participants will be collected at Visits 1 and 2. Hematology and biochemistry tests performed in the local laboratories are listed in Table 10. The volumes of blood to be collected are shown in Table 7.

Table 10 Hematology and Biochemistry Tests

Assay type	System	Component	Method	
Hematology	Whole Blood	Leukocytes (white blood cells)	As per local laboratory	
	Whole Blood	Neutrophils*	procedures	
	Whole Blood	Lymphocytes*		
	Whole Blood	Basophils*		
	Whole Blood	Monocytes*		
	Whole Blood	Eosinophils*		
	Whole Blood	Hemoglobin		
	Thrombocytes	Platelets		
	Red Blood Cells	Erythrocytes (red blood cells)		
Biochemistry	Serum	Blood urea nitrogen	As per local laboratory	
		Alanine aminotransferase (ALT)	procedures	
		Aspartate aminotransferase (AST)		

^{*}For white blood cell differential count.

8.2.3. Study Holding Rules and Safety Monitoring

8.2.3.1. Staggered Enrollment

As this will be the first time that these investigational adjuvanted HPV vaccine formulations will be administered in humans, the enrollment will be staggered (refer to Section 8.2.3.3 for details).

In Step 1, 48 participants (12 per group) aged 18-26 years will be enrolled and vaccinated with the first dose with an interval of at least 60 minutes between participants. Safety data from Step 1 participants will be reviewed 7 days post-dose 1 by an unblinded iSRC (independent of the study team).

The solicited administration site and systemic events that will be collected during the 7-day follow-up period following each vaccination are presented in Table 11. The intensity of the solicited AEs will be assessed as described in Table 12.

Table 11 Solicited Events to be Collected in Step 1 and 2

Event	Symptoms
Solicited administration site events	Pain
	Redness
	Swelling
Solicited systemic events	Fever
	Headache
	Myalgia
	Arthralgia
	Fatigue

Note: participants/participants' parent(s)/LAR(s) will be instructed to measure and record the axillary temperature in the evening. If additional temperature measurements are taken at other times of the day, participants/participants' parent(s)/LAR(s) will be instructed to record the highest temperature in the electronic Diary.

Table 12 Intensity Scales for Solicited Events

Event	Intensity grade	Parameter
Pain	1 (Mild)	Mild: Any pain neither interfering with nor
		preventing normal everyday activities.
	2 (Moderate)	Moderate: Painful when limb is moved and
		interferes with everyday activities.
	3 (Severe)	Severe: Significant pain at rest. Prevents normal
		everyday activities.
Redness and Swelling at	1 (Mild)	>0 mm to ≤20 mm
administration site (Greatest surface	2 (Moderate)	>20 mm to ≤50 mm
diameter in mm)	3 (Severe)	>50 mm
Temperature* in °C	1 (Mild)	\geq 37.5°C (99.5°F) to \leq 38.0°C (100.4°F)
	2 (Moderate)	>38.0°C (100.4°F) to ≤39.0°C (102.2°F)
	3 (Severe)	>39.0°C (102.2°F)
Headache	1 (Mild)	Headache that is easily tolerated
	2 (Moderate)	Headache that interferes with normal activity
	3 (Severe)	Headache that prevents normal activity
Fatigue	1 (Mild)	Fatigue that is easily tolerated
	2 (Moderate)	Fatigue that interferes with normal activity
	3 (Severe)	Fatigue that prevents normal activity
Arthralgia	1 (Mild)	Arthralgia that is easily tolerated
	2 (Moderate)	Arthralgia that interferes with normal activity
	3 (Severe)	Arthralgia that prevents normal activity
Myalgia	1 (Mild)	Myalgia that is easily tolerated
	2 (Moderate)	Myalgia that interferes with normal activity
	3 (Severe)	Myalgia that prevents normal activity

SoA = schedule of activities

*Refer to the SoA (Table 1) for the definition of fever and the preferred location for temperature measurement.

Biochemistry and hematology parameters will be collected in Step 1 participants (refer to Table 10). The intensity of these parameters will be assessed as described in Table 13.

 Table 13
 Biochemistry and Hematology Parameters Grading Component

	Grade 1	Grade 2	Grade 3	Grade 4**
Hematology				
Hemoglobin (g/dL) female	12-11	10.9-9.5	9.4-8	<8
Hemoglobin change from baseline female (g/dL)	<1.5	1.6-2	2.1-5	>5
WBC (cell/mm³) increase	10,800- 15,000	15,001- 20,000	20,001- 25,000	>25,000
WBC (cell/mm ³) decrease	3,500-2,500	2,499-1,500	1,499-1,000	<1,000
Lymphocyte (cell/mm³) decrease	1,000-750	749-500	499-250	<250
Neutrophils (cell/mm³) decrease	2,000-1,500	1,499-1,000	999-500	< 500
Eosinophils (cell/mm³)	650-1,500	1,501-5,000	>5,000	hypereosinophilic syndrome
Platelet (cell/mm³) decrease	140,000- 125,000	124,000- 100,000	99,000- 25,000	<25,000
Biochemistry				
ALT (increase by factor)	1.1-2.5×ULN	2.6-5×ULN	5.1-10×ULN	>10×ULN
AST (increase by factor)	1.1-2.5×ULN	2.6-5×ULN	5.1-10×ULN	>10×ULN
Blood Urea Nitrogen BUN mg/dL	23-26	27-31	>31	Requires dialysis

ALT = alanine aminotransferase; AST = aspartate aminotransferase; BUN = blood urea nitrogen; FDA = Food and Drug Administration; ULN = upper limit of normal; WBC = white blood cells

Note: The laboratory values provided in the table are taken from the FDA Guidance for Industry "Toxicity Grading Scale for Healthy Adults and Adolescent Volunteers Enrolled in Preventive Vaccine Clinical Trials" dated September 2007. These laboratory values serve as guidelines and are dependent upon institutional normal parameters. Institutional normal reference ranges should be provided to demonstrate that they are appropriate.

**The clinical signs or symptoms associated with laboratory abnormalities might result in characterization of the laboratory abnormalities as potentially life-threatening (Grade 4).

Besides the standard AE collection (solicited AEs, unsolicited AEs, SAEs), the study will also collect pIMDs (see Table 21) throughout the study due to presence of the adjuvant AS04.

8.2.3.2. Safety Holding Rules

The safety holding rules for the vaccination phases of the study are defined in Table 14.

For participants enrolled in Step 1, holding rules 1a-1d from Table 14 will be assessed by the investigator on a continuous basis, and meeting any of these holding rules will trigger a hold of vaccination irrespective of number of participants enrolled and/or timing of the event relative to

vaccination. Holding rules 2a-2c from Table 14 will be assessed by the iSRC during the safety evaluations on unblinded data.

These holding rules have been written under the assumption that the safety data from all participants will be available. If the data from all Step 1 participants are not available (i.e., in case a participant is lost to follow-up), then the holding rules will be assessed on a pro-rata basis (expressed as percentage of participants to be evaluated) i.e., 3 out of 12 participants per arm or 25% per arm.

Of note, no formal holding rules will be applied for other safety data such as non-life-threatening SAEs, missed visits due to study intervention-related AEs, Grade 1 and Grade 2 solicited and unsolicited AEs in the 7-day follow-up period and unsolicited AEs collected from Day 8 to Day 30 after study intervention administration. However, if available, these data will also be reviewed by the iSRC to allow an overall assessment of the benefit/risk ratio of study intervention administration.

If the investigator becomes aware of a holding rule being met, they must suspend administration of the study intervention and inform IQVIA immediately (e.g., holding rules 1a-d). IQVIA will inform the investigator if holding rules 2a-c are met. Investigators will be responsible to inform the IRB/IEC if a holding rule has been met.

The following communication sequence must be followed:

- The concerned site staff will put study intervention administration and enrollment on hold.
- The concerned site staff will immediately inform IQVIA's safety team (i.e., the events to be reported via an Electronic Data Capture system [EDC]).
- Enrollment and intervention allocation through IVRS/IWRS will then be stopped on a study level.
- IQVIA will inform all investigators about the stopping of enrollment and intervention.
- IQVIA will also provide the blinded data to GSK's Clinical Research and Development Lead and Safety Lead for further SRT and GSK Global Safety Board review.
- IQVIA will forward the relevant unblinded safety information to iSRC for evaluation.
- Based on the recommendation from iSRC, GSK's Global Safety Board will make the decision whether the study can resume, be modified, or stopped. GSK will notify IQVIA on this decision.
- IQVIA will notify all investigators on this decision.
- Depending on the outcome of the safety evaluation, the study will be re-started, terminated, or resumed under a protocol amendment.

Table 14 Study Holding Rules for Step 1 to be Assessed Post-Dose 1

Holding Rule	Event	Number of participants/group Step 1
la	Death or any life-threatening serious adverse event (SAE)	≥1
1b	Any non-life-threatening SAE that cannot be reasonably attributed to a cause other than intervention as per Investigator or Sponsor assessment	≥1
1c	Any withdrawal from the study (by investigator or participant request) following a Grade 3 adverse event (AE)	≥1
1d	Any administration site or systemic solicited AE leading to hospitalization , or fever > 40°C (104°F), or necrosis at the injection site, each with an event onset within the 7-day (days 1-7) post-intervention period	≥1
2a	Any Grade 3 solicited administration site events (lasting 48 hours or more as Grade 3), with an event onset within the 7-day (days 1-7) post-intervention period	≥3/12 (≥25%)
2b	Any Grade 3 solicited systemic events (lasting 48 hours or more as Grade 3), with an event onset within the 7-day (days 1-7) post-intervention period	≥3/12 (≥25%)
2c	Any Grade 3 unsolicited AE, that can be reasonably attributed to the vaccination as per Investigator or Sponsor assessment, with an event onset within the 7-day (days 1-7) post-vaccination period OR Any Grade 3 or above abnormality in pre-specified hematological or biochemical laboratory parameters with an event onset within the 7-day (days 1-7) post-intervention period	≥3/12 (≥25%)

Note: by Sponsor, it means GlaxoSmithKline Biologicals SA's designee for AE recording and assessment, IQVIA

Risk Assessment for Step 1

As shown in Figure 2, with 12 participants per study group:

- Each holding rule 1a-1d has more than 89% chance of not being met for vaccination with a true incidence rate corresponding to the occurrence of holding rule event below 1%, and has more than 70% chance of being met for vaccination with a true incidence rate above 10%.
- Each holding rule 2a-2c has more than 89% chance of not being met for vaccination with a true incidence rate below 10% and more than 60% chance of being met for vaccination with a true incidence rate above 25%.

[figure not shown]

Figure 2 Probability of Not Meeting Holding Rules 1 and 2 for 12 Participants per Study Group in Step 1

8.2.3.3. iSRC Evaluation

The iSRC will review the accumulated safety data up to 7 days post-dose 1 of sentinel participants in Step 1*. The iSRC will have access to the participant randomization list and will review unblinded data. The iSRC members will determine whether any of the pre-defined holding rules are met (refer to Section 8.2.3) or if there is any other safety signal. If no safety signal is observed, vaccination of the "Step 1" participants will continue, and vaccination of the remaining participants ("Step 2" participants) will be initiated.

Following this initial review(s), the iSRC will review all available safety data on a regular basis (monthly) until data from 1-month post-dose 2 for all participants and data from 1-month post-dose 3 for Step 1 participants are reviewed. During these reviews, monitoring of safety events will be done with no holding rules assessment (refer to the iSRC charter for details). It will be up to iSRC to trigger a study hold or study change if deemed necessary. In addition to the iSRC, the project SRT will review blinded data on a regular basis throughout the study.

*In case not all 48 of the Step 1 participants are enrolled and vaccinated with a first dose of study vaccine by 30 September 2022, the iSRC will review the accumulated safety data up to 7 days post-dose 1 of all participants available by that date. If no safety signal is identified, these participants will be vaccinated with a second dose. To avoid any additional participants running out of the allowed interval range for their second vaccine dose, additional iSRC review(s) may need to be planned to review the safety data up to 7 days post-dose 1 of these participants, but

only when all 48 Step 1 participants have been enrolled and their data have been reviewed by the iSRC, the iSRC will decide on the initiation of the vaccination of Step 2 participants.

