Blood sample collection:

- A 5 mL blood sample will be drawn from Step 1 (Sentinel) participants at Visit 1 (Day 1) and Visit 2 (Day 7) to assess biochemical and hematological parameters.
- For assessment of immune response, blood samples (~50 mL) will be drawn at Day 1, Month 2, Month 3, Month 6, Month 7 and Month 12 in all participants. Immunoglobulin G (IgG) antibody determination will be performed for these timepoints in all participants. Pseudovirion-based neutralization assays will be performed. Blood samples drawn at Day 1 (all participants), Month 2 (at least 96 participants in each group), Month 3 (all participants) and Month 7 (at least 150 participants in each group) will be tested.

Study	Number of	Number of Age	Study	Blinding*	
groups	participants	(Min-Max)	vaccinations	Visit 1 to Visit 7 (Observer- Blind)	
HPV9High	270	16-26 years of age	HPV9-High	X	
HPV9Med	270	16-26 years of age	HPV9-Medium	X	
HPV9Low	270	16-26 years of age	HPV9-Low	X	
Gar9	270	16-26 years of age	Gardasil 9	X	

Table 5 Study Groups, Vaccines, and Blinding

Note: In Germany, only adult participants between and including 18 to 26 years of age will be included in this clinical study.

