7.1. Reference Start Date and Study Day

Study Day will be calculated from the reference start date and will be used to show start/stop day of assessments and events.

Reference start date is defined as the day of the most recent dose of study vaccination and will appear in every listing where an assessment date or event date appears.

If the date of the event is on or after the date of vaccination then:

Study Day = (date of event – date of vaccination) + 1.

If the date of the event is prior to the date of vaccination then:

Study Day = (date of event – date of vaccination).

In the situation where the event date is partial or missing, Study Day, and any corresponding durations will appear partial or missing in the listings.

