7.3. Retests, Unscheduled Visits and Early Termination Data

In general, for by-visit summaries, data recorded at the nominal visit will be presented. Unscheduled measurements will not occur for this study.

Listings will include all scheduled, and early termination discontinuation data.

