7.4. Windowing Conventions

Allowed time window for each visit will be performed as mentioned in "Schedule of Activities", section 1.3 of protocol.

Table C: Intervals Between Study Visits

Interval	Planned Visit Interval*	Allowed Interval Range
Visit 1 → Visit 2	7 days	7 – 12 days
Visit 1 → Visit 3	60 days	56 – 74 days
Visit 3 → Visit 4	28 days	28 – 44 days
Visit 1 → Visit 5 (visit 5 occurring before protocol amendment 2 [08JUN2023])	180 days	180 – 194 days
Visit 1 → Visit 5 (visit 5 occurring on or after protocol amendment 2 [08JUN2023])	180 days	166 – 194 days
Visit 5 → Visit 6	28 days	28 – 44 days
Visit 1 → Visit 7	360 days	346 – 374 days

^{• * =} Number of days between the visits

Document: \\quintiles.net\Enterprise\Apps\sasdata\SAS\\SAS\GlaxoSmithKline\HPV\213749

(HPV9)\Biostatistics\Documentation\SAP\GSK 213749(HPV9-AS04-

001)_WZA97329_SAP_Final_v3.0_02FEB2024.docx

Author: PPD Version Number: 3.0

Version Date: 02FEB2024

Template No.: CS_TP_BS016 Revision 7 Reference: CS_WI_BS005

Page 28 of 48

Table D: Window Convention

Assigned Study Day	Visit Label as per Protocol	Visit Assigned
Day 1	Visit 1	Visit 1
Day 7 (Day 1 + 7 to 12 days)	Visit 2	Visit 2
Day 60 (Day 1 + 56 to 74 days)	Visit 3	Visit 3
Day 88 (Day 1 + 84 to 118 days)	Visit 4	Visit 4
Day 180 (Day 1 + 180 to 194 days) (visit 5 occurring before protocol amendment 2 [08JUN2023])	Visit 5	Visit 5
Day 180 (Day 1 + 166 to 194 days) (visit 5 occurring on or after protocol amendment 2 [08JUN2023])	Visit 5	Visit 5
Day 208 (Day 1 + 208 to 238 days)	Visit 6	Visit 6
Day 360 (Day 1 + 346 to 374 days)	Visit 7	Visit 7

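### Can the Day 7 safety bloods count toward holding rule 2c, when onset is limited to Days 1-7 and the visit may fall 7 to 12 days after vaccination?

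*Protocol*

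**What the plan says.** Rule 2c in Protocol 8.2.3.2, Table 14, has two limbs: related Grade 3 unsolicited events, and laboratory findings. The second limb covers "Any Grade 3 or above abnormality in pre-specified hematological or biochemical laboratory parameters with an event onset within the 7-day (days 1-7) post-intervention period". The threshold is at least 3 of 12 per group. The laboratory bullet in Protocol 9.4.3 uses the same 7-day onset limit.

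The blood is described in Protocol 4.1: "A 5 mL blood sample will be drawn from Step 1 (Sentinel) participants at Visit 1 (Day 1) and Visit 2 (Day 7"). Table 1 requires samples to be drawn before vaccination, so Visit 2 is the only scheduled sample after dose 1. Table 2 plans Visit 2 at 7 days and allows 7 to 12, counted as days between visits. SAP 7.4, Table D, gives "Day 7 (Day 1 + 7 to 12 days").

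Two SAP conventions bear on day counting. SAP 7.1 sets "Study Day = (date of event – date of vaccination) + 1". SAP 7.3 says that in by-visit summaries "data recorded at the nominal visit will be presented". Neither mentions the onset of a laboratory abnormality.

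On the review itself, Protocol 8.2.3.3 states: "The iSRC will review the accumulated safety data up to 7 days post-dose 1 of sentinel participants in Step 1". The risk assessment in 8.2.3.2 gives each of rules 2a-2c "more than 60% chance of being met for vaccination with a true incidence rate above 25" percent.

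**The concern.** Set side by side, the rule's window appears to close just as the only sample is taken. If onset means the date of the draw, a sample at +8 to +12 days is outside Days 1-7 however days are counted. Under the SAP 7.1 formula even a sample at exactly +7 is Study Day 8.

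The stakes would be real. These formulations were being given to humans for the first time, rule 2c holds the only formal laboratory trigger, and the Step 1 review stood before the enrolment of the other 1,032 participants. Entering the same result as an adverse event dated at the draw would not help. The unsolicited limb of rule 2c has the same 7-day limit, and 8.2.3.2 lists "unsolicited AEs collected from Day 8 to Day 30 after study intervention administration" among the data to which no formal holding rule applies.

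**Working it through.** **1. The plan's own figures.** Let X be the number of participants with an event among 12, binomial with rate p. The rule is met if X ≥ 3.
- p = 0.10: P(X ≤ 2) = 0.9^12 + 12(0.1)(0.9^11) + 66(0.1^2)(0.9^10) = 0.2824 + 0.3766 + 0.2301 = 0.889. The protocol states more than 89% for rates below 10%, which agrees after rounding.
- p = 0.25: P(X ≥ 3) = 1 − (0.0317 + 0.1267 + 0.2323) = 0.609. The protocol states more than 60%, which agrees.

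These figures take all 12 participants per group as assessable.

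**2. Permitted Visit 2 days inside Days 1-7.** The permitted elapsed days are 7, 8, 9, 10, 11 and 12.
- Date difference plus 1 (SAP 7.1): Study Days 8 to 13, so 0 of 6.
- Elapsed days: only +7, so 1 of 6.
- Nominal visit label: Day 7 for all, so 6 of 6.

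**3. What the first two readings could cost.** The documents do not report when the Visit 2 samples were taken. Assume that k of 12 samples per group are countable and that the true laboratory rate is 25%. Then P(X ≥ 3) is 60.9% for k = 12, 39.9% for k = 9, 16.9% for k = 6, 1.6% for k = 3, and 0 for k of 2 or fewer. The values of k are illustrations, and the stated 60% is for rule 2c as a whole, not for its laboratory limb. So no stated property is shown to fail.

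**4. Which reading the documents support.**
- The Synopsis, Table 1, Section 4.1, the primary laboratory endpoint in Table 4, Protocol 9.4.1.1 and SAP 17.1.3.4 all treat this sample as the Day 7 measurement. The Synopsis places the Day 7 sampling visit immediately before the committee's review of the first 7 days.
- SAP Table D heads the relevant column Assigned Study Day and gives Visit 2 the value 7. The later visits follow the same pattern: 60 for the planned 60-day interval, 60 + 28 = 88, 180, and 180 + 28 = 208. Under SAP 7.1 a visit exactly 60 days after vaccination would be Study Day 61. The visit labels are therefore planned intervals, not results of the SAP 7.1 formula.
- SAP 5.3 limits the SAP to the interim and final analyses, and SAP 5.1.1 sends the safety committee's analysis to a separate plan. The count of 0 of 6 thus applies a listing convention to a decision that the SAP does not set out to govern.
- A collection-date reading would leave the laboratory limb with almost nothing to count, although the Visit 2 blood was added for the sentinel participants specifically.

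**The case for a change.** The best case for acting is that a holding rule in a first-in-human study should not rest on an unstated convention. SAP 7.1 is the only explicit day formula in either document, and it puts every permitted sample outside the window. SAP 7.3 speaks of summaries, not of onset. Protocol 9.4.3 says that the SAP will describe the committee's analyses in detail, and the SAP passes them on to another plan, so a reader of these two documents cannot confirm how rule 2c was applied. The pro-rata provision in 8.2.3.2 does not settle it either, because its example is a participant lost to follow-up, not a result in hand but dated late.

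What stands is that onset is undefined here and that the rule's window and the visit window are worded differently. Reconciling those passages, and deciding which one governs, is for the sponsor's clinical and safety team. The committee's charter and separate analysis plan are not among these documents and may already do so.

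What does not stand is the step from undefined to unworkable. No passage equates onset with the date of the draw. The committee reviews unblinded data, must also consider any other safety signal under 8.2.3.3, and sees data without a formal rule where available under 8.2.3.2. Rules 1a-1c apply whatever the timing of the event.

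**Conclusion.** No change to the plan follows. This is missing detail that the people applying the rule would fill sensibly: a committee given laboratory results from a visit called Day 7, drawn for its own review, would naturally treat them as the Day 7 results. On that reading all six permitted days count, the 60.9% at a 25% rate is intact, and the effect is zero. The lower probabilities need both a collection-date reading that neither document states and sampling dates that neither document gives.

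Nor would a definition alter the course of the trial. Amendment 3 refers to Month 2 samples already collected, for testing in 384 participants, and Appendix 3 places that subset in Step 2. Step 2 could begin only after the review of all 48 Step 1 participants, so the decision that rule 2c served has been taken. No endpoint, estimate or later dosing decision depends on how laboratory onset is dated.

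The conclusion assumes that the committee had the Visit 2 results before it and counted them by visit. The documents supplied neither confirm nor contradict that.
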